## **8.3 REPORTING OF SERIOUS ADVERSE EVENTS**

Any AE that meets protocol-defined serious criteria or meets the definition of Adverse Event of Special Interest that require expedited reporting must be submitted immediately (within 24 hours of awareness) to OSRO Safety using the CCR SAE report form.

All SAE reporting must include the elements described in Section **9**.

SAE reports will be submitted to the Center for Cancer Research (CCR) at: [[contact]](mailto:[contact]) and to the CCR PI and study coordinator. CCR SAE report form and instructions can be found at:  
<https://ccrod.cancer.gov/confluence/pages/viewpage.action?pageId=157942842>

Following the assessment of the SAE by OSRO, other supporting documentation of the event may be requested by the OSRO Safety and should be provided as soon as possible.

## **8.4 REPORTING PREGNANCY**

### **8.4.1 Maternal Exposure**

If a patient becomes pregnant during the course of the study, the study treatment should be discontinued immediately, and the pregnancy reported to the Sponsor no later than 24 hours of when the Investigator becomes aware of it. The Investigator should notify the Sponsor no later than 24 hours of when the outcome of the Pregnancy become known,

Pregnancy itself is not regarded as an SAE. However, congenital abnormalities or birth defects and spontaneous miscarriages that meet serious criteria (**8.1.2**) should be reported as SAEs.

The outcome of all pregnancies (spontaneous miscarriage, elective termination, ectopic pregnancy, normal birth, or congenital abnormality) should be followed up and documented.

#### 8.4.2 Parental exposure

Male patients should refrain from fathering a child or donating sperm during the study and for 90 days after the last dose of AdHER2 DC vaccine.

Pregnancy of the patient's partner is not considered to be an AE. However, the outcome of all pregnancies (spontaneous miscarriage, elective termination, ectopic pregnancy, normal birth, or congenital abnormality) occurring from the date of the first dose until 90 after the last dose should, if possible, be followed up and documented.

### **8.5 REGULATORY REPORTING FOR STUDIES CONDUCTED UNDER CCR-SPONSOR IND**

Following notification from the investigator, CCR, the IND sponsor, will report any suspected adverse reaction that is both serious and unexpected. CCR will report an AE as a suspected adverse reaction only if there is evidence to suggest a causal relationship between the study product and the adverse event. CCR will notify FDA and all participating investigators (i.e., all investigators to whom the sponsor is providing drug under its INDs or under any investigator's IND) in an IND safety report of potential serious risks from clinical trials or any other source, as soon as possible, in accordance to 21 CFR Part 312.32.

All serious events will be reported to the FDA at least annually in a summary format.

## **9 CLINICAL MONITORING**

As a sponsor for clinical trials, FDA regulations require the CCR to maintain a monitoring program. The CCR's program allows for confirmation of: study data, specifically data that could affect the interpretation of primary and secondary study endpoints; adherence to the protocol, regulations, ICH E6, and SOPs; and human subjects protection. This is done through independent verification of study data with source documentation focusing on:

- Informed consent process
- Eligibility confirmation
- Drug administration and accountability
- Adverse events monitoring
- Response assessment.

The monitoring program also extends to multi-site research when the CCR is the coordinating center.

This trial will be monitored by personnel employed by a CCR contractor. Monitors are qualified by training and experience to monitor the progress of clinical trials. Personnel monitoring this study will not be affiliated in any way with the trial conduct.

## **10 COLLABORATIVE AGREEMENTS**

### **10.1 TECH TRANSFER AGREEMENTS**

Stored samples are being sent to Midissia for testing and characterization of soluble HER2 and anti-HER2 antibodies as a part of this protocol using a Material Transfer Agreement (MTA #42793) which was executed on 09/17/2017. There is also a CDA between Midissia and the NCI (CDA #13887-18, executed 11/10/2017). Additional tech transfers include:

- CRADA # 03048, executed 03/02/2016
- MTA #44020-28, executed 01/24/2018
- MTA #3394-13, executed 11/13/2014
- CRADA #03225, currently being negotiated

## **11 STATISTICAL CONSIDERATIONS**

The primary objectives of this open label, single site, non-randomized, two-part, phase I study of AdHER2 DC vaccination are to determine if the fraction of patients with cardiac toxicity (if it occurs) is sufficiently low to warrant further exploration in subsequent trials and to determine an approximate estimate of the vaccine immunogenicity, as represented by the fraction of patients who develop at least a 3-fold increase in anti-HER2/neu antibody concentration (measured as mcg/mL) or a 4-fold increase in antibody dilution titers over baseline at the time points measured. An important secondary objective is to obtain a preliminary estimate of the proportion of patients who may experience tumor shrinkage or stabilization that is sufficient by modified immune response related criteria (modified irRC) to be considered stable disease, a partial response or better.

It has been reported that up to 7% of patients with HER2/neu expressing tumors treated with trastuzumab monotherapy for metastatic breast cancer developed clinically significant cardiac dysfunction including congestive heart failure. It would be considered acceptable if the therapeutic AdHER2 DC vaccine proposed for this study would produce no greater than that level of cardiac toxicity, but not acceptable if it were to be exceeded. In order to evaluate this using a limited number of patients, a two-part design, but incorporating an early stopping rule, will be implemented.

Statistical considerations pertaining to each part of the study are as follows:

### **11.1 PART I (MAXIMUM OF 30 EVALUABLE PATIENTS)**

The goal of Part I is to investigate vaccine dose escalation and determine whether there is a significant, adverse safety signal regarding cardiac toxicity in patients with recurrent or progressive, metastatic solid tumors as well as adjuvant bladder cancer patients with HER2 expressing tumors that are naive to trastuzumab, lapatinib, ado-trastuzumab and other HER2-directed therapies, in addition to preliminary assessment of the vaccine's immunogenicity and clinical activity. Allowable tumors include breast, ovarian, colon, non-small cell lung, renal cell, bladder and prostate cancer with HER2 characterization by IHC and FISH as outlined in Section **2.1.1.14**.

Inclusion of a broad spectrum of tumors that express HER2 will facilitate more rapid accrual and allow prompt determination of the vaccine's safety and immunogenicity. However, the inclusion

of subjects with multiple tumor types that have varying levels of HER2 expression may preclude identification of an optimal biologically active dose.

During this part, vaccine safety, immunogenicity and preliminary activity will be determined for each dose level given escalating doses of vaccine as follows:

Dose Level 1 (N = 6 patients):	$5 \times 10^6$ viable cells/vaccine
Dose Level 2 (N = 6 patients):	$10 \times 10^6$ viable cells/vaccine
Dose Level 3 (N = 6 patients):	$20 \times 10^6$ viable cells/vaccine
Expansion Cohort (N= 12 patients):	$40 \times 10^6$ viable cells/vaccine

*Dose escalation will proceed as long as 0 of 6 or 1 of 6 patients within a dose level have no evidence of toxicity and at least 3 of the 6 patients within a level have reached Week 12 on study. If 2 of 6 patients on any given dose level develop cardiac toxicity, that dose cohort will be closed to further accrual, no higher doses will be explored, and dose expansion of an additional 12 patients will be enrolled in the next lower dose level to further assess for cardiac toxicity. The vaccine dose at which 0 to 1 of 18 treated patients in Dose Levels 1 to 3 develop cardiac toxicity will be defined as the maximum tolerated dose (MTD). If two or more patients out of 18 at a given dose have developed cardiac toxicity, then the MTD will have been exceeded at that dose, and the dose level below that one will be considered the MTD. Since enrollment in Dose Level 3 has been reached and 0 of 6 patients has toxicity, then an expansion cohort of an additional 12 patients will be added, for a maximum targeted accrual of 30 patients in Part 1. The Expansion Cohort will be treated at  $40 \times 10^6$  viable cells/vaccine and will be monitored for toxicity in an identical manner as previously identified. The 12 patients will be accrued at the  $40 \times 10^6$  level without any planned interim stop, as cardiac toxicity is not presently anticipated given the results as of 12/11/15. With all 12 enrolled as a single cohort, there is a 4.9% probability of having 2 or more of 12 patients with cardiac toxicity if the true probability for a given patient is 3%, and 55.7% of having 2 or more of 12 with cardiac toxicity if the true probability for a given patient is 15%. Therefore, observing 0-1 of 12 with toxicity would be acceptable, and  $40 \times 10^6$  would be considered the maximum evaluated and tolerated dose. If we observe 2 or more with cardiac toxicity at or before accruing the 12th patient, this exceeds a safe level. Further patients would be added subsequently, by amendment, to the next lower dose, to confirm its safety.*

***To ensure that the trial does not continue to accrue patients in the event that a much greater incidence of toxicity than expected would be recognized early, the following early stopping rules for accrual will be invoked in each part of the study if:***

- *Two or more of 6 patients in a given dose develop evidence of cardiac toxicity, accrual will be stopped to that dose level. Accrual expansion of an additional 12 patients will occur in the next lower dose level to further evaluate for cardiac toxicity.*
- *Any death (unrelated to underlying primary disease) that occurs and is attributed as being possible, probably or definitely related to the investigational AdHER2 DC vaccine (FDA requirement).*

## 11.2 PART II (MAXIMUM OF 30 EVALUABLE PATIENTS)

Since the risk for cardiac toxicity may differ in individuals who have previously received HER2-directed therapy, the FDA is requesting that repeat dose escalation of AdHER2 DC vaccination be conducted in Part II of the study *in a population with prior exposure to trastuzumab, pertuzumab, lapatinib, ado-trastuzumab emtansine (TDM1) and other HER2-directed therapies.* This population will include adults with recurrent or progressive, metastatic breast, gastric/gastroesophageal or other cancers with 1+ to 3+ HER2/neu expression by IHC or an equivocal or positive FISH result. Vaccine dose escalation will be repeated to again determine whether there is an adverse safety signal regarding cardiac toxicity, in addition to assessment of the vaccine's immunogenicity and clinical activity. Vaccine dose escalation, administration, re-staging assessment and early stopping rules that will be invoked that are identical to that conducted in Part I.

The goal is to accrue up to 30 evaluable patients in Part II of the study and treat them with the experimental AdHER2 vaccine.

Unless an early stopping rule is invoked in either Part I or Part II of the study, the number of patients who have experienced a clinically significant cardiac toxicity will be determined to estimate the frequency of cardiac toxicity. In addition, the dose level(s) at which toxicity is observed will also be examined.

*If in part I, dose escalations have taken place in the first three dose levels and 0 of 20 patients have experienced cardiac toxicity, Part II of the study in patients with metastatic breast cancer and prior exposure to HER2-directed therapies will proceed with vaccine dosing based on the safety confirmed in Part I and as outlined in Section 3.1.2.* A maximum accrual of 30 patients will be enrolled in Part II and patients will continue to enroll on that dose unless 3 patients have experienced cardiac toxicity.

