### **Proposed Dosage and Administration**

Part II of the study will enroll 30 breast, gastric/gastroesophageal or other cancer patients as outlined in the vaccine dose cohorts outlined below:

Dose Level 1 (N = 6 patients):  $20 \times 10^6$  *viable* cells/vaccine

Expansion Cohort (N = 24 patients):  $40 \times 10^6$  *viable* cells/vaccine

Autologous AdHER2 DC vaccine will be administered intradermally at Weeks 0, 4, 8, 16 and 24. Re-staging will be performed as outlined in Section **6.2**. Vaccine dose escalation will follow the revised procedures specified in Section **3.1.2**.

Abbreviated Title: AdHER2/neu DC Vaccine

Version Date: 07/22/2019

Figure 11: AdHER2 Autologous DC Vaccine Study Schema

	Screen Consent Baseline	Week 0	Week 4	Week 8	Week 12	Week 16	Week 20	Week 24	Week 28	Week 32	Week 36	Week 40	Week 48	Week 60	Week 76	Week 100	Week 124
Vaccine		V	V	V	V	V	V										
Echo	V		V	V	V	V	V	V	V	V	V	V	V	V	V	V	V
Scans	V			V	V	V	V	V	V	V	V	V	V	V	V	V	V
Correlatives	V			V	V	V	V	V	V	V	V	V	V	V	V	V	V

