### **Early stopping rules for accrual will be invoked in each part of the study if:**

- **Two or more of 6 patients in a given dose level develop evidence of cardiac toxicity, accrual will be stopped to that dose cohort. Accrual expansion of an additional 12 patients will occur in the next lower dose level to further evaluate for cardiac toxicity.**
- **Any death (unrelated to underlying primary disease) that occurs and is attributed as being possibly, probably or definitely related to the investigational AdHER2 DC vaccine (FDA requirement)**

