Dose escalation will proceed in groups of 6 patients. *Dose escalation will proceed as long as 0 to 1 of 6 patients at given dose level have no evidence of toxicity and at least 3 of the 6 patients at the dose level have reached Week 12 on study.* If 2 of 6 patients on any given dose level develop cardiac toxicity, that dose cohort will be closed to further accrual, no higher doses will be explored, and dose expansion of an additional 12 patients will be enrolled in the next lower dose level to further assess for cardiac toxicity. *The vaccine dose at which 0 to 1 of 18 treated patients in Dose Levels 1 to 3 develop cardiac toxicity will be defined as the maximum tolerated dose (MTD). If two or more patients out of 18 at a given dose level have developed cardiac toxicity, then the MTD will have been exceeded at that dose, and the dose level below that one will be considered the MTD.* Since enrollment in Dose Level 3 has been reached and 0 of 6 patients has toxicity, then an expansion cohort of 12 patients, will be added for a maximum targeted accrual of 30 patients in Part I. The 12 patients will be accrued at the  $40 \times 10^6$  dose level without any planned interim stop, as cardiac toxicity is not presently anticipated given the results as of 12/11/15. With all 12 enrolled as a single group, there is a 4.9% probability of having 2 or more of 12 patients with cardiac toxicity if the true probability for a given patient is 3%, and 55.7% of having 2 or more of 12 with cardiac toxicity if the true probability for a given patient is 15%. Therefore, observing 0-1 of 12 with toxicity would be acceptable, and  $40 \times 10^6$  would be considered the maximum evaluated and tolerated dose. If we observe 2 or more with cardiac toxicity at or before accruing the 12th patient, this exceeds a safe level. Further patients would be added subsequently, by amendment, to the next lower dose, to confirm its safety.

If dose escalation has proceeded in the first three dose levels in Part I and 0 of 20 patients have experienced cardiac toxicity, Part II of the study in patients with metastatic breast, gastric, gastroesophageal junction or other cancers and prior exposure to HER2-directed therapies will proceed with vaccine dosing based on the safety confirmed in Part I and outlined in Section 3.1.2. A maximum accrual of 30 patients will be enrolled in Part II.

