## **11.4 STUDY TERMINATION**

This study will be terminated for the following reasons:

- Completion of enrollment accrual and all scheduled monitoring studies for enrolled subjects.
- Development of clinically significant CTRCD toxicity (defined as a decrease in the LVEF of > 10 percentage points, to a value < 53%) in two or more of the first 10 patients enrolled in the study or four or more of the first 20 patients enrolled in the study.
- Failure to accrue study subjects in a timely manner.

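### Part II carries two cardiac accrual rules that disagree at two events among the first six patients of the 24-patient expansion, and the three-event count has no stated denominator

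*Combined protocol and SAP*

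**What the plan says.** Section 11.1 introduces its accrual limits with the words "the following early stopping rules for accrual will be invoked in each part of the study if", and the first limit reads: "Two or more of 6 patients in a given dose develop evidence of cardiac toxicity, accrual will be stopped to that dose level". Section 3.1.1 gives the same rule: "Two or more of 6 patients in a given dose level develop evidence of cardiac toxicity, accrual will be stopped to that dose cohort".

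Section 11.2 carries this into Part II, referring to "early stopping rules that will be invoked that are identical to that conducted in Part I". The last sentence of that section gives the 30-patient maximum for Part II and adds that "patients will continue to enroll on that dose unless 3 patients have experienced cardiac toxicity".

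The dosing list for Part II in section 3.1 has six patients at Dose Level 1 and then "Expansion Cohort (N = 24 patients"). Section 2.4.1 repeats these numbers as upper limits. The parallel Part II paragraph in section 3.1.2 says "A maximum accrual of 30 patients will be enrolled in Part II" and has no three-event clause.

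Section 11.3 gives probabilities for three or more events in 30 patients, labelled as illustrative. It also says that zero to two events in 30 would have been acceptable under the design as first planned.

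**The concern.** Cardiac safety is a primary objective. Section 11.2 gives a possibly different cardiac risk after prior HER2-directed therapy as the reason for repeating dose escalation in Part II. Section 12.5 says that a vaccine-induced immune response cannot be withdrawn as a drug can, and relies on the stopping rules for protection.

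Suppose two of the first six patients in the Part II expansion develop cardiac toxicity. Sections 3.1.1 and 11.1 close that dose to accrual. The last sentence of section 11.2 keeps it open until a third event. Both sentences govern enrolment at a dose, and nothing says which one prevails. Staff and the safety committee would have to choose between them after seeing the events, which is what a prespecified rule is meant to prevent. The missing denominator raises a second question: three events among the 24 patients at the expansion dose is a different limit from three among all 30.

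**Working it through.** **Inputs.** Part II cohorts of 6 and 24 (sections 2.4.1 and 3.1); limits of 2 of 6 (sections 3.1.1 and 11.1) and 3 events (section 11.2); true rates of 3% and 15% (section 11.3) and 7%, the acceptability limit in section 11. Assumptions: patients are independent, the rate is the same at both doses, and 2 of 6 means the first six patients at a dose. X is the number of events and p the true rate; results are given for 3% / 7% / 15%.

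**Step 1: the plan's own figure.** Section 11.3 prints 6% and 85% for three or more of 30 at 3% and 15%.
- P(X ≥ 3 | 30) = 1 − [P(0) + P(1) + P(2)]
- At 3%: 1 − (0.40101 + 0.37207 + 0.16686) = 0.0601
- At 15%: 1 − (0.00763 + 0.04040 + 0.10337) = 0.8486

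Both reproduce. At 7%: 1 − (0.11337 + 0.25599 + 0.27939) = 0.3513. The printed arithmetic is right; the fault is in the rules.

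**Step 2: the state in which the rules disagree.**
- P(X = 2 | 6) = 15 p²(1 − p)⁴
- At 7%: 15 × 0.0049 × 0.7481 = 0.0550
- Results: 1.2% / 5.5% / 17.6%

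**Step 3: three events counted over the expansion only.**
- P(X ≥ 3 | 24) at 7%: 1 − (0.17522 + 0.31653 + 0.27399) = 0.2343
- Results: 3.4% / 23.4% / 72.0%, against 6.0% / 35.1% / 84.9% over all 30

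**Step 4: add 2 of the first 6 at either dose to 3 of 30.** The only new way to reach a limit is exactly two events in one of the two groups of six and none in the other 24 patients.
- Added probability = 2 × P(X = 2 | 6) × (1 − p)²⁴
- At 3%: 2 × 0.01195 × 0.48142 = 0.0115
- At 7%: 2 × 0.05498 × 0.17522 = 0.0193
- At 15%: 2 × 0.17618 × 0.02023 = 0.0071
- Totals: 7.2% / 37.1% / 85.6%

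**Step 5: keep 2 of the first 6, but count the three events within each dose.**
- P(limit reached) = 1 − P(X ≤ 1 | 6) × Σ over x = 0, 1 of P(X = x | 6) P(X ≤ 2 − x | 18)
- At 7%: 1 − 0.93918 × 0.75085 = 0.2948
- Results: 5.3% / 29.5% / 79.0%

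Steps 4 and 5 both keep the two-of-six rule and differ only in the denominator for the third event.

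**The case against.** The strongest defence is a staged reading: two of six is an early check and three of 30 an overall limit. It has support. The 30-patient maximum is in the same sentence as the three-event clause. Section 11.3 uses three or more of 30 and calls zero to two of 30 acceptable. Section 11.1 describes the two-of-six rule as a guard against toxicity that shows itself early, and section 11.2 speaks of an early stopping rule being invoked in either part. A denominator of 30 can therefore be inferred, and under it the two-of-six rule adds little (step 4).

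The defence does not settle the matter. The section 11.3 calculation is labelled illustrative and assumes 18 + 6 + 6 patients without intermediate looks, not 6 + 24. The statement about zero to two of 30 concerns Part I. The clause itself speaks of enrolment at one dose, which does not fit a count pooled over two. The remark in section 11.2 about invoking an early rule concerns estimation, not accrual. No section says whether two of six applies within the 24.

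Three stronger readings are tempting, and the documents do not support them.
- **The rules collide equally at both Part II doses.** Dose Level 1 is full at six, so after six patients there is no further accrual there to continue, and section 11.1 bars higher doses at two of six. At most, a few unfilled places are affected if both events come before the sixth enrolment.
- **The reading with three events at either dose and no two-of-six rule is equally open.** It gives 1 − P(X ≤ 2 | 6) × P(X ≤ 2 | 24), or 23.9% at 7%, but section 11.2 expressly adopts the Part I early rules.
- **Section 11.4 adds a further conflict in Part II.** It terminates the study on events in "two or more of the first 10 patients enrolled in the study or four or more of the first 20 patients enrolled". Section 11.3 reports 20 patients already enrolled and dosed by 12/11/15, and FDA approval to start Part II enrolment came on 12/14/15. Part II patients cannot be among the first 20.

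**Conclusion.** The contradiction is real and stands in current operative text. It is confined in practice to two events among the first six patients of the Part II expansion, a state with probability 1.2% / 5.5% / 17.6% at true rates of 3% / 7% / 15%.

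The unstated denominator has the larger effect. At the plan's own 7% limit, three or more events has probability 23.4% over the 24 expansion patients and 35.1% over all 30. With the two-of-six rule kept at both doses, the contrast is 29.5% against 37.1%. The printed 6% and 85% describe the three-event limit only if it is counted over all 30 with no other rule acting.

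These figures rest on independent patients, a common rate at both doses, and two of six read as the first six at a dose. The contradiction itself depends on none of these rates. Because it affects a stopping rule for a primary safety objective and is cheap to remove, it should be resolved before the rule is needed.

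**What to change.** Reconcile sections 3.1.1, 3.1.2, 11.1 and 11.2 so that the Part II cardiac accrual rules do not contradict one another. The text should state:
- what the three events are counted over: the patients at one dose, or all 30;
- whether two of six applies within the 24-patient expansion;
- which rule takes precedence if more than one is kept. An early rule and an overall limit can coexist if their order is stated.

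Give exact binomial probabilities for the rules kept, over the actual 6 + 24 structure. Which rules to keep is for the sponsor and the FDA.

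Two minor items belong in the same amendment. Section 11.1 says the Part I expansion is monitored in the same way as before and also that it has no planned interim stop; these statements need reconciling. The escalation sentence in sections 3.1.2, 3.2 and 11.1 is inverted: as written, it lets escalation proceed when none or one of six patients is free of toxicity. The intent is recoverable from the two-of-six sentence that follows it in sections 3.1.2 and 11.1.

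The cost is amendment wording and a few exact probabilities, some of which may look less favourable than those printed. No patients, procedures or new stopping rules are added.
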